Official title: Stereotactic body radiation therapy with sequential S-1 for patients with locally advanced pancreatic cancer and poor medical conditions --a phase II clinical trial (SILAPANC trial)

NCT number: NCT02704143

Document state: 9th May 2020

1. Participants and eligibility

To be eligible for inclusion in the SILAPANC trial, all patients with clinical suspicion for pancreatic cancer, as presented in the imaging studies, were required to receive pathological examinations. If deemed necessary, further high-quality dedicated imaging of the pancreas should be performed before patients are enrolled into the study and undergo any study-related procedures. Biopsies were performed with fine needle aspiration *via* endoscopic ultrasound by experienced gastroenterologists. Specimen sections would be evaluated by two independent pathologists. After confirmed diagnosis of locally advanced pancreatic cancer by pathological examinations, patients should have the willingness and ability to provide an informed consent and comply with subsequent treatment plans, tests and other study procedures.

The following inclusion and exclusion criteria would be employed to preserve high internal validity and reduce risks of SBRT or S-1-induced adverse effects.

Inclusion criteria:

1. Unresectable without metastasis:

(a) Pancreatic head/uncinate process:

- (i) Solid tumor contact with the superior mesenteric artery $>180^\circ$;
- (ii) Solid tumor contact with the celiac axis $>180^\circ$;
- (iii) Solid tumor contact with the first jejunal superior mesenteric artery branch;
- (iv) Unreconstructible superior mesenteric vein/portal vein due to involvement or occlusion (can be due to tumor or bland thrombus);
- (v) Contact with most proximal draining jejunal branch into the superior mesenteric vein.

(b) Pancreatic body/tail:

- (i) Solid tumor contact of $>180^\circ$ with the superior mesenteric artery branch;
- (ii) Solid tumor contact with the celiac axis and aortic involvement;
- (iii) Unreconstructible superior mesenteric vein/portal vein to tumor involvement or occlusion (can be due to tumor or bland thrombus).

2. Without any other treatment before SBRT.

3. A life expectancy of >3 months.

4. ECOG: 2 or 3 points.

5. Age of more than 18 years old.

6. Blood routine examination: Absolute neutrophil count (ANC) $\geq 1.5 \times 10^9$ cells/L, leukocyte count $\geq 3.5 \times 10^9$ cells/L, platelets $\geq 70 \times 10^9$ cells/L, hemoglobin ≥ 8.0 g/dL.

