7. Liver and kidney function tests: Albumin > 2.5 g/dL, total bilirubin < 3 mg/dL, creatinine < 2.0 mg/dL, AST $< 2.5 \times$ ULN (Upper Limit of Normal) (0-64 U/L), ALT $< 2.5 \times$ ULN (0-64 U/L).

8. INR < 2 (0.9-1.1).

9. Ability of the research subject or authorized legal representative to understand and the willingness to sign a written informed consent document.

Exclusion criteria:

1. Prior surgery, chemotherapy or radiation for the pancreatic cancer.
2. Evidences of metastatic disease such as nodal or distant metastases by abdomen CT and chest CT or FDG PET-CT.
3. Contraindication to receiving radiotherapy.
4. ECOG: 0-1 point.
5. Age<18
6. Abnormal results of blood routine examinations, liver and kidney function and coagulation tests.
7. Patients with active inflammatory bowel diseases or peptic ulcer.
8. Gastrointestinal bleeding or perforation within 6 months.
9. Heart failure: NYHA III-IV.
10. Women who are pregnant.
11. Participation in another clinical treatment trial while on study.
12. Patients in whom fiducial implantation was not possible.
13. Inability of the research subject or authorized legal representative to understand and the willingness to sign a written informed consent document.

Due to better diagnostic yield, safety and the potential lower risk of peritoneal seeding, endoscopic ultrasound-guided fine-needle aspiration is preferred for all patients

suspected of pancreatic cancer.

2. Doses of S-1

The doses of S-1 are calculated by the body surface. Hence, patients will receive S-1 orally, twice daily, at a dose of 80 mg/m^2 for 28 days, followed by a 14-day interval, which would repeat for 6 cycles. It was initiated one month after SBRT.

3. CT simulation for treatment planning

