After CT simulation, CT images are transferred to the workstation where the target volumes are contoured by an attending radiation oncologist. Gross tumor volume (GTV) is delineated as a radiographically evident gross disease by contrast CT acquired from the portal-venous phase. At the discretion of the physician, clinical target volume (CTV) encompassing areas of the potential subclinical disease spread is also designated. In most cases, the CTV equals GTV. A 2-5 mm expansion margin is included to determine the planning target volume (PTV). When the tumor is adjacent to critical organs, the expansion of CTV should be avoided. Therefore, an individualized treatment plan would be developed based on tumor geometries and locations. Ninety percent of PTV should be covered by the prescription dose. The prescription isodose line is limited to 70-75%, which would restrict the tumor D_{max} . If dose level violates the constraint of SBRT, the patient would be considered as ineligible for this trial. The prescribed dose of PTV varies from 35-40Gy/5f with a single dose of 7-9Gy. In particular, these doses would be reduced if the tumor is approximately one-third or more of the duodenum or stomach circumference, or if the tumor abuts the bowel in only one area, as determined by the relationship of the tumor to the duodenum in axial, coronal and sagittal planes in CT scans, or the space between the tumor and the bowel wall is <3 mm. Normal tissue constraints are according to the American Association of Physicists in Medicine

guidelines in TG-101.

6. Follow-up

Patients are re-evaluated after Cyberknife every one month for the first three months, every 2-3 months for the next two years, and every six months for a total three years. Remissions of symptoms and radiation-related toxicities would be assessed. In addition, they would undergo laboratory tests, physical examinations, analysis of quality of life, and imaging studies every month within the first three months. Subsequent examinations in later follow-ups are the same.

7. Statistical analysis

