All outcomes would be analyzed based on intention-to-treat principle. Continuous and categorical data were expressed as median (interquartile range, IQR) and n (%), respectively. Overall survival and progression free survival are calculated *via* the Kaplan-Meier method compared by the log-rank test. A two-sided α of less than 0.05 was considered statistically significant. Statistical testing is performed using SPSS version 20.0 (IBM Corp, Armonk, NY, USA).

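### Section 6 limits toxicity assessment to radiation-related events, and nothing provides for S-1-related or all-cause adverse events to be graded or reported, so reported toxicity could understate that of SBRT plus S-1

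*Combined protocol and SAP*

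**What the plan says.** Section 6 (Follow-up) sets the toxicity scope in one sentence: "Remissions of symptoms and radiation-related toxicities would be assessed". The same section schedules visits monthly for three months and then "every 2-3 months for the next two years". It lists laboratory tests, physical examination, quality of life and imaging for the monthly visits, and adds "Subsequent examinations in later follow-ups are the same".

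Section 2 (Doses of S-1) makes S-1 part of the regimen, given "for 28 days, followed by a 14-day interval, which would repeat for 6 cycles". On timing it says "It was initiated one month after SBRT".

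Section 1 (Participants and eligibility) mentions harm from S-1 once, as a reason for the entry criteria, which are meant to "reduce risks of SBRT or S-1-induced adverse effects". It admits patients with "ECOG: 2 or 3 points".

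Section 7 (Statistical analysis) names two outcomes: "Overall survival and progression free survival are calculated". It adds an intention-to-treat sentence covering all outcomes and generic descriptive summaries (median with interquartile range; n with %). It names no toxicity variable.

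**The concern.** The regimen under study has two components, and the toxicity to be assessed is defined by attribution to one of them. From about one month after SBRT a patient may have an adverse event caused by radiation, by S-1 or by the cancer itself. Under the Section 6 wording, whether that event counts depends on a judgement of cause, and the plan gives no rule for making it. An event judged to be due to S-1, or of unclear cause, has no stated place in the record.

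This matters more because patients are selected for poor performance status, so how well they tolerate the whole regimen is central to reading the results. A toxicity figure built on radiation-attributed events alone could be taken as the toxicity of SBRT plus S-1.

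There is also a gap in ascertainment. The plan does not say that a visit covers events since the previous one. Once visits are 2-3 months apart, the interval is longer than a 42-day S-1 cycle, and a short-lived event between visits could go unrecorded.

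**Working it through.** **Text comparison.** The plan states no toxicity rate, sample size or safety target, so there is no figure to reproduce. The check is what each section provides on toxicity.

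| Section | Provision on toxicity |
|---|---|
| 1 | S-1 and SBRT adverse effects named as a reason for the eligibility criteria; nothing on assessment |
| 2 | S-1 dosing and start; nothing on recording toxicity |
| 3-5 | Simulation, tracking and planning; normal-tissue dose constraints, but no grading or reporting of toxicity |
| 6 | Radiation-related toxicities assessed; laboratory tests, examination and quality of life done, but not linked to adverse-event recording |
| 7 | Overall and progression-free survival named; generic summaries; no safety outcome |

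No grading scale, attribution rule, collection window or safety denominator appears anywhere, for radiation events or for others. No sign of redaction suggests that such text was removed.

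**S-1 exposure against the visit schedule (context only).** This describes visit frequency. It does not measure the scope problem and does not size any understatement.

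Inputs: six cycles of 28 days on and 14 off (Section 2); start one month after SBRT (Section 2); monthly visits to month 3, then every 2-3 months (Section 6). Assumptions: one month = 30 days, S-1 starts on day 30, and all six cycles are completed.

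- Cycle length: 28 + 14 = 42 days.
- Cycle starts: days 30, 72, 114, 156, 198, 240.
- Planned dosing days: 6 × 28 = 168, the last on day 240 + 27 = 267.
- Dosing days up to and including the day-90 visit: 28 (days 30-57) + 19 (days 72-90) = 47.
- Dosing days after it: 168 − 47 = 121, and 121/168 = 72.0%.

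Sensitivity to the length of a month:

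| Month | Dosing days after the month-3 visit | Share of 168 |
|---|---|---|
| 28 days | 125 | 74.4% |
| 30 days | 121 | 72.0% |
| 31 days | 119 | 70.8% |

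Sensitivity to completion (30-day month): a patient who stops after three cycles has 3 × 28 − 47 = 37 of 84 dosing days after day 90 (44%). One who stops after two has 2 × 28 − 47 = 9 of 56 (16%). The 72% is therefore a figure for full completion, in a population whose entry criterion asks only for a life expectancy above three months.

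**The case against.** The strongest reply is that the plan does observe patients on S-1. Laboratory tests, examinations and quality of life are repeated at later visits, so effects such as low blood counts would often be seen. Section 7 covers all outcomes and gives n (%) for categorical data, which could be read to include toxicity. Section 1 shows that S-1 harm was in mind, and investigators may in practice record everything.

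Much of this stands, and it limits the harm. A reader might infer that S-1 toxicity will go unseen, and the document does not support that. What remains is that seeing an abnormal result is not the same as grading and reporting it as toxicity, and that the only toxicity the plan defines, whatever Section 7 covers, is radiation-related.

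A second reply is that too much rests on one adjective: radiation toxicity also lacks a scale, a window and a summary, so the general defect is an unspecified safety outcome. That is correct and belongs in the point. It does not cancel the scope problem, because adding a scale and a table to the present sentence would still leave S-1 events outside it.

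A third reply is that the 72% concerns visit spacing. That also stands. The radiation-only wording would be just as deficient with a visit in every cycle. A reader might take 72% as the share of S-1 toxicity that would be missed; nothing in the document supports that reading.

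**Conclusion.** The point holds as a risk and should be corrected. Section 6 states a positive scope for toxicity that covers one of two study treatments, and no other section fills the gap. Followed literally, events attributed to S-1 or of unclear cause could be left out, and the reported toxicity could understate that of SBRT plus S-1.

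It would go too far to say that reported toxicity will be understated. The document does not show what will be tabulated, and it gives no toxicity rates or sample size from which a shortfall could be calculated. The only calculable figure is the contextual one, 121 of 168 planned dosing days (72%; 71-74% across month lengths of 28 to 31 days). It rests on S-1 starting one month after SBRT and on all six cycles being completed.

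**What to change.** **Section 6.** Replace the reference to radiation-related toxicities with: 'all adverse events regardless of attribution, graded on a named scale and version, from the start of SBRT through the end of S-1 and follow-up, each visit covering events since the previous visit'. Parts of the document are in the past tense, so some patients may already have been treated. For them, take events from existing records, label them as collected retrospectively, and note that records may under-ascertain events.

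**Section 7.** Report the proportion of patients by worst grade from any cause, with a 95% confidence interval, among all patients who start SBRT. As a secondary rate, report events with onset on or after the first S-1 dose among those who start S-1. The onset rule is needed so that events from before S-1 are not counted. State that this is a selected group, since these patients had to reach S-1. Say that these denominators are an exception to the intention-to-treat sentence. Give radiation-attributed and S-1-attributed events in secondary tables. A headline threshold (for example grade 3 or higher) and an exact (Clopper-Pearson) interval are options; the plan sets neither.

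**Cost.** Wording in two sections and a larger adverse-event record, including questions or record review for the time between visits. Recall may still miss mild, short-lived events. On the same patients, scale, threshold and period, the all-cause rate cannot be lower than the radiation-only rate. No dose or visit frequency changes.

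### Intention to treat is applied to every outcome, so S-1 or whole-regimen toxicity percentages would count patients who never started S-1 as free of its harm

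*Combined protocol and SAP*

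**What the plan says.** Section 7 (Statistical analysis) reads: "All outcomes would be analyzed based on intention-to-treat principle". Categorical data are summarised as counts and percentages. The section does not define the intention-to-treat set, a safety set or any as-treated set.

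Section 6 (Follow-up) names the toxicity to be assessed: "Remissions of symptoms and radiation-related toxicities would be assessed". S-1 adverse effects appear only in Section 1, where the eligibility criteria are justified as a way to "reduce risks of SBRT or S-1-induced adverse effects".

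Section 2 (Doses of S-1) gives the schedule, "for 28 days, followed by a 14-day interval, which would repeat for 6 cycles", and the start: "It was initiated one month after SBRT". The inclusion criteria in Section 1 admit patients with "ECOG: 2 or 3 points" and "A life expectancy of >3 months".

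Section 5 (Treatment planning and target delineation) makes a patient ineligible if the SBRT plan breaks a dose constraint. That can be known only after fiducial placement and simulation. The plan does not say whether such a patient stays in the intention-to-treat set.

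**The concern.** Intention to treat suits survival, because it keeps everyone for whom the strategy was intended. For toxicity it has a perverse effect: a patient who never received a component cannot be harmed by it, yet stays in the denominator as a patient without the event. The fewer patients who reach a component, the safer that component looks.

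The design leaves two points at which exposure can fail. The first is before SBRT, between enrolment and the first fraction. The second is the month between SBRT and S-1, in frail patients with limited life expectancy. Tolerability is a central question in this population, and S-1 is half of the regimen named in the trial title. A toxicity percentage that falls as delivery fails would mislead readers on that question.

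**Working it through.** The plan states no toxicity rate, sample size or share of patients reaching S-1, so there is no figure of its own to reproduce. The check gives the form of the bias and its size under stated assumptions. The intention-to-treat set is taken to be all enrolled patients, since the plan does not define it.

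**Inputs from the documents.** S-1 starts 1 month after SBRT, in 6 cycles of 28 + 14 = 42 days (Section 2). Entry requires ECOG 2 or 3 and life expectancy above 3 months (Section 1).

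**Assumed inputs.** A true S-1 toxicity rate of p = 30% among patients who start S-1, and exponential survival from SBRT with a median of 6, 9 or 12 months.

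**Step 1: form of the bias.** Let u be the share of enrolled patients who never start S-1. They contribute no S-1 events, so

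rate over all enrolled = p × (1 - u).

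For a whole-regimen percentage, irradiated non-starters can still contribute radiation events. If their rate is r, the reported rate is p(1 - u) + r·u, which is short by u(p - r). Provided r does not exceed p, the direction is the same and the shortfall is no larger than for S-1 alone.

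**Step 2: share lost to death before S-1.** With median m in months, u = 1 - 0.5^(1/m).

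| Assumed median | u | 30% reads as |
|---|---|---|
| 6 months | 10.9% | 0.30 × 0.891 = 26.7% |
| 9 months | 7.4% | 0.30 × 0.926 = 27.8% |
| 12 months | 5.6% | 0.30 × 0.944 = 28.3% |

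**Step 3: sensitivity to u, whatever its cause.** With u = 0 the rate stays at 30%. With u = 5%, 10%, 20% or 30% it reads 28.5%, 27%, 24% or 21%. The last two need losses beyond those in Step 2, from decline or refusal, which the documents do not quantify.

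**Step 4: radiation-related toxicity.** Every irradiated patient is already exposed when the S-1 interval begins, so that interval does not dilute this rate. Only enrolled patients who were never irradiated could. If their share is v, the factor is (1 - v). The documents give no value for v and do not say whether patients found ineligible at planning are counted.

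**Step 5: course length.** Six cycles take 6 × 42 = 252 days, or 8.3 months (238 days, or 7.8 months, to the last dosing day). The course therefore runs about 8 months and ends about 9 months after SBRT. A patient who dies or stops during it has had shorter exposure but is not unexposed, so course length does not enter u.

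**The case against.** The strongest reply is that the only toxicity the plan names is radiation-related, and a late S-1 start cannot dilute that. This is correct, and it limits the point. A reader might infer that the month's delay biases the radiation toxicity rate; the documents do not support that. What remains is any S-1 or whole-regimen percentage. S-1 is in the title, its adverse effects are an acknowledged concern in Section 1, and follow-up visits with laboratory tests cover the S-1 period. If such a percentage is reported, Section 7 prescribes the all-enrolled denominator.

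A second reply is that SBRT non-exposure is partly handled, since patients who fail planning are declared ineligible, failed fiducial placement is an exclusion, and follow-up is counted from SBRT. That may keep v small. It does not settle who is in the set.

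A third reply concerns size. The life-expectancy criterion is meant to screen out early deaths, so a constant hazard probably overstates them. That stands: the 6 to 11% is illustrative, and u could be close to zero.

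Two further inferences should be resisted. Setting a course that ends about 9 months after SBRT against a life expectancy of just over 3 months may suggest that much of the cohort is unexposed; in fact it shows shortened exposure. Nor does incomplete treatment undermine the survival analysis: intention to treat estimates the effect of the planned strategy, including incomplete delivery. A landmark analysis from S-1 start would be a preference and would not correct the toxicity denominator.

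**Conclusion.** The point holds in a limited form. Section 7 puts toxicity under intention to treat and offers no treated-patient denominator. Any S-1 toxicity percentage over all enrolled patients is biased downward by (1 - u), and a whole-regimen percentage is biased in the same direction by no more than that. With assumed medians of 6 to 12 months, deaths alone put u at about 6 to 11%, so 30% would read as about 27 to 28%. Decline or refusal would lower it further, by an amount the documents do not fix.

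The direction is certain whenever anyone fails to start S-1 and some starters have S-1 toxicity. The size is modest, and it rests on an assumed toxicity rate, assumed medians, a constant hazard, and an intention-to-treat set made up of all enrolled patients. For radiation-related toxicity the only exposure gap is among enrolled patients never irradiated, whose place in the set is unstated.

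**What to change.** In Section 7:

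- Limit the intention-to-treat rule to OS and PFS, and state who is in that set, including whether patients found ineligible at SBRT planning remain in it.
- Report radiation-related toxicity among patients who received at least one SBRT fraction.
- Report toxicity from S-1 start among patients who took at least one S-1 dose. Beside it, give the number starting S-1 and the cycles received, so that readers can see how selected the starters are and how much exposure the percentage reflects.

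In Section 6, name S-1 toxicity as an assessed outcome, so that the third item has a stated basis.

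The cost is a few sentences and one extra table. The denominators and cycle counts come from treatment records. S-1 adverse events must also have been recorded at follow-up, which the documents imply but do not state. Reported toxicity percentages will become slightly less favourable. No treatment rule changes.

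### Section 7 gives radiation toxicity only a crude n (%), which understates cumulative toxicity if patients are lost or analysed early, and which carries no time point

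*Combined protocol and SAP*

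**What the plan says.** Section 7 (Statistical analysis) is one short paragraph. Three of its statements bear on toxicity.

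- Population: "All outcomes would be analyzed based on intention-to-treat principle".
- Description: "Continuous and categorical data were expressed as median (interquartile range, IQR) and n (%), respectively".
- Time-to-event methods: "Overall survival and progression free survival are calculated" by Kaplan-Meier. No other outcome is given a method that handles censoring.

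Section 6 (Follow-up) states that "Remissions of symptoms and radiation-related toxicities would be assessed". After monthly visits for the first three months, the schedule is "every 2-3 months for the next two years, and every six months for a total three years".

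Neither section gives a denominator for toxicity, a grading scale, an acute or late window, a rule for patients lost or with short follow-up, or a data cut-off. Death is not mentioned as an event that ends the time at risk of toxicity.

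**The concern.** Whether a patient has had toxicity, or its worst grade, is a categorical variable, so under Section 7 it would be summarised as n (%). With intention-to-treat applied to every outcome, the natural denominator is everyone enrolled. Radiation toxicity can appear at any point in three years and is seen only at attended visits. A patient who stops attending, or who enrolled shortly before the analysis, stays in the denominator but cannot contribute a later event. The plan handles this problem for survival and leaves it open for safety.

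Any resulting error runs in the unsafe direction: more loss, or an earlier analysis, makes the treatment look safer. In addition, a percentage with no time attached cannot be read as a 3-, 12- or 36-month risk. That second defect remains even when follow-up is complete.

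**Working it through.** The plan states no toxicity rate, expected survival, loss rate, accrual period or cut-off, so there is no figure to reproduce. What follows is an illustration, and every rate in it is an assumption.

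**Inputs**

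- Horizon T = 36 months, from Section 6.
- Toxicity hazard t = 0.02 per month (assumed, constant from the start).
- Median survival 9 months (assumed), so the death hazard is d = ln 2 / 9 = 0.0770 per month. The population criteria (ECOG 2 or 3; "A life expectancy of >3 months") make early death likely but give no median.
- Loss hazard l, varied. A yearly loss of p corresponds to l = -ln(1 - p)/12.

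**Formulas**

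- True cumulative incidence, death competing: t/(t+d) × [1 - exp(-(t+d)T)].
- Crude n (%) over all enrolled: t/(t+d+l) × [1 - exp(-(t+d+l)T)].

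**True value.** 0.02/0.0970 × [1 - exp(-0.0970 × 36)] = 20.0%.

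**Crude value under loss**

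| Assumed loss | l per month | t+d+l | Crude n (%) | Shortfall relative to 20.0% |
|---|---|---|---|---|
| None | 0 | 0.0970 | 20.0% | 0% |
| 5% per year | 0.0043 | 0.1013 | 19.2% | 4% |
| 10% per year | 0.0088 | 0.1058 | 18.5% | 7.5% |
| 20% per year | 0.0186 | 0.1156 | 17.0% | 15% |
| 3% per month | 0.0300 | 0.1270 | 15.6% | 22% |
| 5% per month | 0.0500 | 0.1470 | 13.5% | 32% |

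The last two rows are severe: they equal about 30% and 45% per year among those still at risk (1 - exp(-0.36) and 1 - exp(-0.60)), and lose 23% and 34% of all patients before toxicity or death. For median survival of 6 to 12 months, the shortfall at 3-5% monthly loss is 18-36%.

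**Earlier horizons.** With 3% monthly loss and median survival of 9 months, the crude figure is low by about 4%, 8% and 13% of the true risk at 3, 6 and 12 months (at 12 months, 12.3% against 14.2%).

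**Early analysis with no loss.** If the data were analysed on the day a uniform 36-month accrual closed, crude n (%) would be 0.206 × [1 - (1 - exp(-3.49))/3.49] = 14.9%, against 20.0%. This is an extreme case. As a milder one, set the true 36-month risk to 10%, accrual to 24 months and the cut-off to 6 months after the last entry. The crude figure is then 6.6-8.7% for median survival of 6 to 18 months. If toxicity can start only after month 6, it is 5.3-6.4% for median survival of 9 to 18 months.

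**Role of death.** A patient who dies without toxicity is correctly counted as event-free in a cumulative incidence, so deaths do not create this bias. For the same reason, one minus Kaplan-Meier with deaths censored is not a suitable replacement: with these inputs it would give 1 - exp(-0.02 × 36) = 51%, against the true 20.0%.

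**The case against.** A reader might infer that the plan counts lost or recently enrolled patients as toxicity-free, and hence that late toxicity is understated. The documents do not support that. The n (%) sentence is a general rule for descriptive data and does not mention toxicity. No sentence fixes the toxicity denominator or the handling of missed assessments. No early cut-off is planned and no loss rate is given. If every patient is followed to death or 36 months, crude n (%) is exactly right. Death is probably the main reason for short follow-up in this population, and it does no harm here.

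Three further objections have weight. The large shortfalls need heavy loss or a very early analysis; ordinary yearly loss costs 4-15% of the true risk. The constant hazard from the start is a poor model of late toxicity. A cumulative incidence that censors at the last assessment assumes loss is unrelated to toxicity, and frail patients may stop attending because they are unwell, so the remedy may not remove all of the bias.

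It can also be argued that counts by worst grade are a legitimate summary, and that a grading scale and time windows should be settled first. Both are fair, and the counts should stay. None of this supplies the missing method: as written, Section 7 offers nothing that allows for unequal follow-up when toxicity is reported.

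**Conclusion.** The point holds in conditional form. Section 7 contains no toxicity analysis that allows for loss, early analysis or competing death, and n (%) over all enrolled patients is the natural reading of what it does contain. The direction of any error is known: downward. Its size is not, because it depends on a loss rate and a cut-off that the documents do not give. Under the assumed inputs (2% per month, median survival 9 months) it runs from zero with complete follow-up, through about 4-15% of the true risk with 5-20% yearly loss, to 22-32% with 3-5% monthly loss. The lack of a time point does not depend on these assumptions. This is a cheap improvement to reporting, and does not show that the trial's toxicity figures are wrong.

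**What to change.** In Section 7:

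- Keep the count of patients by worst toxicity grade, and state its denominator.
- Add the cumulative incidence of radiation toxicity by the Aalen-Johansen method, with death without toxicity as a competing event and censoring at the last toxicity assessment.
- Report it at 3, 6 and 12 months after SBRT, and at later times such as 24 and 36 months where the number at risk allows, with 95% confidence intervals and numbers at risk. Under the assumed 9-month median only about 6% would be alive at 36 months (exp(-0.0770 × 36)), so the late estimates may be imprecise.
- State the number lost to follow-up and the data cut-off.
- State that the estimate assumes non-informative loss.

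The cost is a little programming outside the SPSS version named in Section 7, and recording the date of each toxicity and of each last assessment. After month three, onset would be known only to within a visit interval of two to six months. The reported toxicity figure may be less favourable. Treatment, visits and sample size do not change.
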